### 8.1 Analysis Sets

- *Safety*: all participants who receive any IP
- *All Enrolled*: all participants who signed informed consent

### 8.2 Missing Data Handling

All possible procedures within Good Clinical Practice (GCP) will be used to minimize Post-dosing Early Termination. All participants who receive IP in at least one Experimental Session will be included in all safety analyses.

#### 8.2.1 Partial or Missing Dates

The following conventions will be used to impute missing portions of dates for AEs and concomitant medications. Note that the imputed values outlined here may not always provide the most conservative date. In those circumstances, the imputed value may be replaced by a date that will lead to a more conservative analysis.

**Start Dates:**

1. If the year is unknown, then the date will not be imputed and will be assigned a missing value.
2. If the month is unknown, then:
  - a. The month and day of the first dose date will be imputed if the year matches the first dose date year.
  - b. Otherwise, 'January' will be assigned.
3. If the day is unknown, then:
  - a. The day of the first dose date will be imputed if the month and year match the first dose date month and year.
  - b. Otherwise, the first day of the month will be assigned.

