**Stop Dates:**

1. If the year is unknown, then the date will not be imputed and will be assigned a missing value.
2. If the month is unknown, then 'December' will be assigned.
3. If the day is unknown, then the last day of the month will be assigned.

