### **8.8.2 Analysis of Adverse Events**

The primary measure of safety will be the reporting of unsolicited AEs. All AEs collected from Enrollment to Termination will be categorized as follows:

- Pretreatment AEs are defined as AEs that occur during the Preparatory Period prior to the first dose in the first Experimental Session
- Treatment Emergent AEs are defined as AEs that occur during the Treatment Period from the first Experimental Session to the last Integrative Session
- AEs that occur on and two days after MDMA administration
- AESIs are defined as AEs specified in the protocol related to cardiac function and abuse liability
- Follow-up Period AEs are defined as AEs that occur during the Follow-up Period after the last Integrative Session through Termination
- AEs leading to discontinuation of IP
- AEs resulting in death or hospitalization.
- SAEs
- AEs continuing at Termination.

Verbatim terms on case report forms will be mapped to preferred terms (PT) and system organ class (SOC) using the Medical Dictionary for Regulatory Activities (MedDRA) Version 24.0. Frequency and incidence of AEs will be displayed by PT, sorted by SOC, severity, and seriousness. AEs will be analyzed and presented as follows:

- If a participant has more than one AE mapped to the same PT, that AE will be reported once using the highest severity
- Relationship will be determined by the Clinical Investigator
- AEs that occur on day of Experimental Sessions and two days after IP administration will be presented separately.

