### **8.8.3 Concomitant Medications**

Frequency and incidence of concomitant medications will be displayed by generic name, sorted by class, and summarized by treatment group, analysis set, and category. Concomitant medications taken on Day 0 (Experimental Session), Day 1, Day 2 after IMP administration will be presented separately. Any psychiatric concomitant medications will be tabulated by period (Preparatory, Treatment Period, Follow-up Period). Frequency and incidence of positive or serious ideation and suicidal behavior will be presented using descriptive statistics of C-SSRS scores in tabular format. Vital signs (heart rate, blood pressure, and body temperature) for Experimental Sessions will be summarized using descriptive statistics in tabular format listing values at pre-IMP administration, prior to the supplemental dose, and at the end of each Experimental Session.

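### The SAP 8.2.1 start-date rules ignore a known stop date, so a record that ended before the first dose can be given a start after its own stop; a resolved pre-dose AE would then become a Day 0 treatment-emergent AE

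*SAP*

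**What the plan says.** SAP 8.2.1 states its scope as follows: "The following conventions will be used to impute missing portions of dates for AEs and concomitant medications". Its start-date list has two branches that insert the first dose date.

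- Rule 2a, month unknown: "The month and day of the first dose date will be imputed if the year matches the first dose date year".
- Rule 3a, day unknown: "The day of the first dose date will be imputed if the month and year match the first dose date month and year".

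When the year does not match, rule 2b applies: "Otherwise, 'January' will be assigned". When the month and year do not match, rule 3b uses the first of the month. Stop dates have their own list, for example "If the day is unknown, then the last day of the month will be assigned". Nothing links the two lists, and nothing requires the start to be on or before the stop.

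The section notes that an imputed date may not be the most conservative one and adds: "In those circumstances, the imputed value may be replaced by a date that will lead to a more conservative analysis".

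These dates feed tables that divide at the first dose. SAP 8.8.2 says "Pretreatment AEs are defined as AEs that occur during the Preparatory Period prior to the first dose in the first Experimental Session" and places treatment-emergent AEs from the first Experimental Session onward. SAP 8.8 and 8.8.3 show AEs and medications on Days 0, 1 and 2 separately. SAP 8.8.3 also tabulates psychiatric medications by Preparatory, Treatment and Follow-up period.

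**The concern.** Setting a partial start date to the first dose date is a usual cautious convention when it is unclear whether an event began before or after dosing. Here there can be no such doubt: a complete stop date before the first dose proves that the record was pre-dose, yet the rule still moves its start to the dosing day.

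This design generates pre-dose records. Protocol 4.2 has psychoactive drugs tapered and washed out before Visit 3, and Protocol 7.3.1 puts the first dose 1 to 14 days after Visit 3. Protocol 11.1 collects all medications from Screening. Protocol 7.1.5 starts AE collection at enrollment, and Protocol Table 9 expects tapering to bring new or returning symptoms.

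At stake is the boundary between pretreatment and treatment-emergent events, and the Day 0 tables. They serve safety objectives 3, 4, 8 and 9, under an overall aim of supporting the package insert.

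**Working it through.** The SAP gives no figure to reproduce, so the check applies its rules literally.

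**Algebra.** Let F be the first dose date, T the recorded stop and S* the imputed start. Under rules 2a and 3a, S* = F. If T < F, then S* − T = F − T > 0. Every record that meets the matching condition and stopped before F therefore gets a start after its stop. Rules 2b and 3b give the earliest date consistent with the recorded parts, so they cannot produce this contradiction.

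**Worked cases** (assumed first dose 20 May 2022):

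| Record | Recorded start | Recorded stop | Rule | Imputed start | Result |
|---|---|---|---|---|---|
| Drug | 2022 | 25 Apr 2022 | 2a | 20 May 2022 | 25 days after stop |
| AE | 2022 | 2 May 2022 | 2a | 20 May 2022 | 18 days after stop |
| AE | May 2022 | 12 May 2022 | 3a | 20 May 2022 | 8 days after stop |
| Drug | 2019 | 25 Apr 2022 | 2b | 1 Jan 2019 | no error |
| AE | Apr 2022 | 12 May 2022 | 3b | 1 Apr 2022 | no error |
| AE | 2022 | 1 Jun 2022 | 2a | 20 May 2022 | no contradiction |

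**Effect on classification.** Judged by start date, the first three records fall on Day 0 and in the Treatment Period. Judged by whether the interval from start to stop overlaps the period, they fall in no period, because the interval is negative.

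**How often the rule bites, given a partial start.** The documents do not give the number of partial dates, so these are shares among such records only, and each rests on an assumption.

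- *Drugs, year-only start.* Suppose first doses are spread evenly over the year and the drug began t years earlier. The chance that both fall in the same year is 1 − t for t < 1, and 0 otherwise. Average this over t from 45 days (45/365 = 0.123) to an upper limit:
  - 6 months: 1 − (0.123 + 0.5)/2 = 0.69.
  - 12 months: 1 − (0.123 + 1)/2 = 0.44.
  - 24 months: [(1 − 0.123)²/2]/(2 − 0.123) = 0.384/1.877 = 0.20.
- *AEs, day-only missing, resolved before dosing.* With onsets uniform before dosing and mean duration 3 to 7 days, the share wrongly dated to the first dose is about 70–72% for a 14-day window, 42–45% for 30 days, 18–22% for 60 days and 12–14% for 90 days.
- *All start–stop pairs weighted equally, every first-dose date in one year.* With only the day missing, the share is 88%, 25% and 5% for look-backs of 5, 35 and 77 days. With the month missing, it is 99%, 94% and 86%. Five days is the minimum Preparatory Period in Protocol 4.2, and 77 days is the 11-week upper limit in Protocol Table 1.

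For day-only-missing AEs the share runs from 5% to 88% depending on the assumed window, so none of these figures is an estimate for this trial.

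**The case against.** The strongest reply is about consequence and size.

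**Tapered drugs.** A reader might infer that they are necessarily counted as on-treatment. The documents do not support that. SAP 8.8.3 refers to medications taken on a given day, not begun on it, and states no start-date algorithm. A programmer testing for overlap would not place a drug with a pre-dose stop on Day 0. This stands: what is certain for drugs is an impossible record, not a miscount.

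**Frequency.** A reader might also infer that most participants who taper are affected. No passage says that start dates are often partial. Protocol Table 9 mentions long-prescribed medications in earlier sponsor trials, and a drug begun in an earlier year goes to January of that year without error. For AEs, onset date is a required item (Protocol 10.1) and AEs are asked about at each Preparatory Session (Protocol 7.2), so partial onsets may be few. Taper and washout end before Visit 3, so the 14-day window fits taper-phase AEs poorly. All this stands.

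**Safeguards.** Source data verification and central monitoring (Protocol 14.2) and physician review of medications (Protocol 11.1) may query an impossible recorded pair. They do not remove this error: the recorded data are merely incomplete, and the contradiction is created at analysis by the imputation.

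**The override.** It permits a replacement, but it is optional and does not define conservative. In safety work, counting an event as treatment-emergent is usually the conservative choice, so the clause gives no reason to undo the error.

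**Direction.** The error over-counts treatment-emergent AEs in a single-arm descriptive summary. It hides no harm and alters no between-arm comparison. This limits the importance but does not make the rule right.

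**Conclusion.** The defect is real and follows from the text alone: rules 2a and 3a can date the start of a record after its known stop. For AEs, a resolved pre-dose event then enters the treatment-emergent and Day 0 tables. This assumes classification by start date, which SAP 8.8.2 implies but does not spell out. For medications, it is confined to drugs begun in the first-dose year and stopped before dosing; misassignment in the Day 0 and by-period tables is possible but depends on an algorithm that the SAP leaves open.

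The number of affected records cannot be determined from the documents, and the percentages above should not be quoted as expected rates. The effect is limited to descriptive safety and concomitant-medication tables. A reader might infer that the effectiveness results are compromised; they are not, since these rules cover only AE and medication dates, and PCL-5 and SDS do not depend on them. The point is worth correcting because a stated rule gives a demonstrably wrong result and the correction costs very little.

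**What to change.** Add to the Start Dates rules in SAP 8.2.1:

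> An imputed start date may not be later than the recorded stop date. If the stop date shows that the record ended before the first dose, the first dose date is not imputed; the earliest date consistent with the recorded parts is used (for AEs, not earlier than informed consent), and the record is classified as Pretreatment/Preparatory.

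The consent floor is needed because Protocol 10.1 collects AEs only from signed consent, and a bare January or first-of-month fallback could date an AE before that.

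In the worked cases, the drug recorded as 2022 moves to 1 January 2022. The AE recorded as May 2022 moves to 1 May 2022, or to the consent date if later. The AE recorded as 2022 moves to 1 January 2022 or the consent date, whichever is later. Records that stop on or after the first dose do not change.

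The cost is a short SAP addition and a small programming check before database lock. Slightly fewer records count as treatment-emergent, and only those whose own stop date proves they were pre-dose.

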7.3.1 Experimental Sessions

There will be three open-label Experimental Sessions (Visits 4, 8, 12). Procedures for MDMA-assisted therapy will remain the same across all sessions and all procedures regardless of dose received. Experimental Sessions must be at least 6 hours long, measured from 30 minutes prior to IMP administration. The Experimental Sessions will consist of:

- Experimental Session 1 (Visit 4) will occur 1 to 14 days after Preparatory Session 3 (Visit 3). The first Experimental Session will include 80 mg of MDMA followed by a supplemental half-dose 1.5 to 2 hours after the initial dose unless tolerability issues emerge with the first dose or it is refused by the participant.
- Experimental Session 2 (Visit 8) will occur 21 to 56 days after Experimental Session 1 (Visit 4) and 1 to 14 days after Integrative Session 1.3 (Visit 7). A dose of 80 or 120 mg MDMA will be administered. A supplemental dose (40 mg or 60 mg) will be administered 1.5 to 2 hours after the initial dose unless tolerability issues emerge with the first dose or it is refused by the participant. If the participant received an initial dose of 80 mg, a 40 mg supplemental dose will be used. If the participant received an initial dose of 120 mg, a 60 mg supplemental dose will be used. If drug supply does not permit availability of 60 mg capsules, a reduced supplemental dose of 40 mg may be administered following the 120 mg initial dose.
- Experimental Session 3 (Visit 12) will occur 21 to 56 days after the second Experimental Session (Visit 8) and 1 to 14 days after Integrative Session 2.3 (Visit 11). A dose of 80 or 120 mg MDMA will be administered. A supplemental dose (40 mg or 60 mg) will be administered 1.5 to 2 hours after the initial dose unless tolerability issues emerge with the first dose or it is refused by the participant. If the participant received an initial dose of 80 mg, a 40 mg supplemental dose will be used. If the participant received an initial dose of 120 mg, a 60 mg supplemental dose will be used. If drug supply does not permit availability of 60 mg capsules, a reduced supplemental dose of 40 mg may be administered following the 120 mg initial dose.

Table 7: Schedule of Procedures for Experimental Sessions

Approximate Time during an 8 hour session	Procedure or Action
9:30	Urine drug screen and pregnancy test, concomitant medication information
	collected, participant acclimated to environment, C-SSRS. Begin video
	recording.

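### The rule for a missing AE start day refers only to the first of three doses, so most Day 0 to 2 events of Sessions 2 and 3 with an unknown day would leave the Day 0 to 2 tables

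*SAP*

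**What the plan says.** SAP 8.2.1 sets the conventions for incomplete AE and concomitant medication dates. For a start date with the day unknown there are two branches:

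- AE in the month of the first dose: "The day of the first dose date will be imputed if the month and year match the first dose date month and year".
- AE in any other month: "Otherwise, the first day of the month will be assigned".

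If the month is unknown as well, the anchor is again the first dose: "The month and day of the first dose date will be imputed if the year matches the first dose date year". The introduction to 8.2.1 concedes that these values may not be the most conservative and adds: "In those circumstances, the imputed value may be replaced by a date that will lead to a more conservative analysis". It does not say what triggers a replacement, which date is then used, or who decides.

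Protocol 7.3.1 schedules three Experimental Sessions, the second and third each 21 to 56 days after the one before. Safety objective 4 (Protocol 2.3, SAP 3.3) is the incidence of treatment-emergent events during a session and one and two days after dosing. SAP 8.8.2 accordingly states: "AEs that occur on day of Experimental Sessions and two days after IP administration will be presented separately". SAP 8.8 and Protocol 13.2.2 ask for the same display by Day 0, 1 and 2.

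**The concern.** Anchoring on the first dose suits a drug that is started once. Here there are three separate doses, and the display in question is defined relative to each of them. Sessions 2 and 3 usually fall in a later calendar month than Session 1, so an event just after one of them, with its day unknown, is sent to the 1st of that month. That is normally outside the three-day window to which the event belongs.

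The same event after Session 1 stays in its window. The loss therefore falls only on Sessions 2 and 3, the sessions at which the dose regimen (Protocol 4.6) permits the higher initial dose. What is at stake is the Day 0 to 2 tabulation and any comparison between sessions drawn from it, not the overall AE counts.

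**Working it through.** The documents give no figure on this point, so there is none to reproduce. I applied the written rule by enumeration.

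**Inputs**
- Three sessions, successive gaps of 21 to 56 days (Protocol 7.3.1).
- Window: session day plus two days (SAP 8.8.2).
- Missing-day rule of SAP 8.2.1, override not used.
- My assumptions: first-session date uniform over 365 days; both gaps uniform over 21 to 56 days; true onset equally likely on Day 0, 1 or 2; events tabulated by onset date.

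**Step 1: share placed in the correct window (Sessions 2 and 3).** Outside the first-dose month, the imputed 1st lies in the right window only in these cases, per calendar month:
- session on the 1st: all 3 onset days;
- session on the second-to-last day: Day 2 only (1 case);
- session on the last day: Days 1 and 2 (2 cases).

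That is 3 + 1 + 2 = 6 per month. Over a year, 12 × 6 = 72 of 365 × 3 = 1,095 combinations, and 72 / 1,095 = 6.6%.

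**Step 2: share placed in another session's window.** This happens, for example, when Session 2 falls in the same month as Session 1 and the event is moved to the first dose date. The shares come from the enumeration.

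**Step 3: share outside every window** = 100% − correct − other session.

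| Gaps | Session | Correct | Other session | Outside all |
|---|---|---|---|---|
| 21 to 56 days | 1 | 100% | 0% | 0% |
| 21 to 56 days | 2 | 6.6% | 5.5% | 87.9% |
| 21 to 56 days | 3 | 6.6% | 2.6% | 90.8% |
| 28 days | 1 | 100% | 0% | 0% |
| 28 days | 2 | 6.6% | 11.2% | 82.2% |
| 28 days | 3 | 6.6% | 8.9% | 84.5% |

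At the extremes, with every gap 21 days the share outside is 59.2% (Session 2) and 83.6% (Session 3). With every gap 56 days it is 93.4% for both.

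**Examples**
- Doses on 10 March, 7 April and 5 May; event on 8 April, day missing. It becomes 1 April, six days before the second dose, and leaves the table.
- Doses on 5 and 28 March; event on 29 March, day missing. It becomes 5 March and stays in the table, but as Session 1 Day 0.

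**Step 4: treatment-emergent status.** In no combination does the imputed date of a true Day 0 to 2 event precede the first dose, so these events remain treatment-emergent.

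**Step 5: the proposed rule.** I imputed the latest session date in the recorded month, otherwise the 1st, without using stop dates. The share outside all windows is 0% for every session. The share in the correct session's window is 94.5%, 94.5% and 100% for Sessions 1, 2 and 3 with 21 to 56 day gaps, and 88.8%, 88.8% and 100% with 28-day gaps. The remaining errors, 100 − 94.5 = 5.5% and 100 − 88.8 = 11.2%, arise when two sessions share a month. If every gap were 21 days the error would be 100 − 65.8 = 34.2% for Sessions 1 and 2.

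**The case against.** The strongest reply is that hardly any event will be affected. AEs are recorded at the end of each session (Protocol 7.3.1), at the visit next morning (7.3.3) and by telephone every other day for 14 days (7.3.2). Onset date is a required item (10.1). A Day 0 to 2 event with an unknown day should be rare. This stands, and it sets the weight of the point.

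Second, the SAP allows a more conservative date. That softens the rule but does not cure it, because the clause is optional and names no trigger and no replacement date. A reader might infer that the choice would be made after looking at the data; the SAP does not say when it would be made.

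Third, the result depends on counting by onset. SAP 8.8.2 speaks of events that occur on those days, while objective 4 speaks of events reported then. If events still present in the window were counted, one imputed to the 1st and continuing to the session would stay in the table.

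Fourth, the rule does not lean one way. A reader might infer that it makes the drug look safer in general. It does not: a missing day in the first-dose month puts any event, even one from the Preparatory Period, on Session 1 Day 0. With the month missing too, about 90% of Session 2 and 81% of Session 3 Day 0 to 2 events land in some Day 0 to 2 window, almost all as Session 1 Day 0. (Those two figures assume first sessions from July 2021 to June 2022.) The loss described here belongs to the missing-day case.

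**Conclusion.** The point holds as a minor defect. Followed as written, the missing-day rule takes about 88% (Session 2) and 91% (Session 3) of the affected Day 0 to 2 events out of the Day 0 to 2 tables, or 82.2% and 84.5% with 28-day gaps, and none for Session 1. About 7% land correctly and about 3% to 11% land in another session's window. This rests on uniform dates and gaps, tabulation by onset and no use of the override. The documents do not say how often days are missing, so no count of events can be given.

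Some stronger readings are not supported:

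- It is not true that all such events are lost. About 93% are misplaced (100 − 6.6 = 93.4%), but some of these stay in the tables under the wrong session.
- Overall counts do not suffer: these events remain treatment-emergent, and SAE and AESI totals do not depend on the Day 0 to 2 split.
- For an unknown year the SAP says "If the year is unknown, then the date will not be imputed and will be assigned a missing value". A reader might infer that such an AE cannot be treatment-emergent, but no section says that a missing date excludes it, and with an average participation of 22 weeks (Protocol 4.2) an unknown year is unlikely.
- The medication table needs no parallel change on this ground. It counts medications taken on those days, and a start on the 1st with a missing stop day set to month end already spans the session.

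**What to change.** In SAP 8.2.1, for AEs with the start day missing:

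1. Impute the most recent Experimental Session date in the recorded month that is not after the AE stop date. If there is none, use the 1st of the month.
2. State how months containing two sessions are handled.
3. State that for the Day 0 to 2 tables this rule replaces the discretionary substitution of a more conservative date.

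The cost is a few lines of SAP text and a small programming change. There are two side effects. Some events from other days of the month will be counted on a session day, which is the conservative direction for these tables. In addition, about 5% to 11% of the affected Session 1 and Session 2 events may be assigned to the wrong session when two sessions share a month. That range ignores stop dates. A known stop date before the later session prevents this error, so the condition in item 1 can only reduce it.
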